5.11. Follow-Up

Subjects with successful GORE® Carotid Stent implant will return for follow-up at 30 days, 6 months, 1, 2 and 3 years. Subjects considered Technical Failures (no GORE® Carotid Stent implant) are only required to complete a 30 day follow-up and will have then completed the study.

The following assessments are required for each follow-up visit (unless indicated otherwise):

- Exam and vital signs
- NIHSS
- Modified Rankin Scale
- Carotid Duplex Ultrasound of target vessel
- Concomitant medications (antiplatelet or anticoagulant therapy) assessment
- Adverse events assessment

GORE CONFIDENTIAL INFORMATION

Follow-up Visit Windows

The follow-up visits should be completed within an acceptable time frame and in accordance with the protocol defined visit windows. All intervals are to be calculated from the index procedure. The 6-Month visit target is 180 days. The yearly visits are calculated on a calendar year from index procedure.

30 Days	6 Months (180 Days)	1 Year	2 & 3 Years
\pm 7 days	\pm 14 days	\pm 30 days	\pm 45 days

If the visit is not able to be completed during these windows the visit should be completed as soon as possible; however, it will be considered a protocol deviation and should be reported per local IRB policy.

5.12. Subject Withdrawal from the Clinical Study

A subject may withdraw from the clinical study at any time and should notify the Investigator in this event. The Investigator may also withdraw the subject from the clinical study at any time based on his/her medical judgment. The Investigator will encourage subjects to return for all required follow-up visits.

All subjects who withdraw from the study should complete an end of study visit. No further visits are required by the subject once the end of study visit is complete.

5.13. Subject Lost to Follow-Up

The Investigator should encourage subjects to return for the required follow-up visits. These measures are important as the clinical study objectives may not be realized if a large number of subjects are lost to follow-up (LTF).

A subject may withdraw from the clinical study at any time and should notify the Investigator in this event. If a subject refuses to return for the follow-up visits, the Investigator will attempt to obtain at least vital status and whether or not the subject has experienced a stroke or TIA. In the event of subject death, a death certificate or autopsy report should be obtained to confirm cause of death and reported on the Subject Completion / Discontinuation Form.

A subject will be considered LTF and discontinued from the study once they have missed two required follow-up visits and three documented attempts for each pending study related visit have been made by the Investigator to contact the subject.

One of the three documented attempts must include a certified (traceable) letter. The Investigator must complete the appropriate CRF (CRF Study Completion / Discontinuation Form) documenting the subject's withdrawal or discontinuation from the clinical study. The subject will be considered withdrawn once the Sponsor receives the respective CRFs.

GORE CONFIDENTIAL INFORMATION

The Investigator may also withdraw the subject from the clinical study at any time based on the Investigator's medical judgment.

The study Monitor will ensure that subject withdrawals are documented properly, discussed with the Investigator, and reported to the Sponsor

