#### 4.3 **Primary Endpoint**

The primary endpoint of 1-year MAE will be calculated as a subject-based binomial proportion. The numerator will be the count of subjects who experience death, any stroke, or MI through 30 days post-index procedure, or ipsilateral stroke through one year (365 days) post-index procedure. The denominator will be the count of subjects free of MAE and with clinical follow-up of at least 335 days post-index procedure, plus the count of subjects in the numerator. Only MAE adjudicated by the CEC will be used in this analysis. Acceptable clinical follow-up includes the Subject Evaluation CRF, duplex ultrasound, modified Rankin scale, and NIHSS.

A one-sided 95.1% upper confidence bound will be calculated (using the standard error based on  $H_0$ ) and compared to the prespecified performance goal. If this bound is less than the performance goal, then the primary endpoint is met and the test device will have demonstrated acceptable performance. The *P* value for the corresponding one-sided normal

approximation to the binomial test will be reported. The primary hypothesis test will use  $\alpha$ =0.049 to ensure an overall Type-1 error rate  $\leq$ 0.05.

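### Lost-to-follow-up and investigator-withdrawal rules can end an implanted subject's follow-up before 1 year with no duty to establish stroke status to day 365

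*Protocol*

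**What the plan says.** Protocol 5.11 sets the schedule: "Subjects with successful GORE® Carotid Stent implant will return for follow-up at 30 days, 6 months, 1, 2 and 3 years". Two of these visits fall before the 1-year visit. On timing, it says "The 6-Month visit target is 180 days", with a window of 14 days either side; the 1-year window is 30 days either side.

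Protocol 5.13 treats a subject as lost and discontinued "once they have missed two required follow-up visits and three documented attempts for each pending study related visit have been made". It adds: "One of the three documented attempts must include a certified (traceable) letter". The two missed visits need not be consecutive.

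Protocol 5.12 gives a second route: "The Investigator may also withdraw the subject from the clinical study at any time based on his/her medical judgment". No criteria are listed, and 5.13 repeats the permission. After a withdrawal, "No further visits are required by the subject once the end of study visit is complete".

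For the primary endpoint, SAP 4.3 says: "The denominator will be the count of subjects free of MAE and with clinical follow-up of at least 335 days post-index procedure", to which subjects with an event are added whatever their length of follow-up. Only events adjudicated by the Clinical Events Committee (CEC) count.

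**The concern.** The endpoint includes ipsilateral stroke from day 31 to 1 year, so every implanted subject needs a known stroke status over that whole period. Under either route, collection can stop earlier without the subject withdrawing consent.

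Once it stops, other sections leave a later stroke no stated way into the analysis. Protocol 9.1.3 collects adverse events only up to completion or discontinuation. Protocol 9.4 and SAP 3.4 start adjudication only after a site reports a potential event. SAP 4.3 counts only adjudicated events.

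SAP 4.2.1 times the primary analysis for when endpoint status is known for all enrolled and implanted subjects, and these rules work against that aim. With one arm and a fixed goal, no control group shares the losses.

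**Working it through.** The plan states no figure on this point that could be reproduced. The performance goal, expected rate and any loss allowance are not visible in the available text. The check is therefore visit-window arithmetic, followed by an illustration on assumed rates.

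**Windows** (Protocol 5.11, SAP 3.2), closing day:
- 30 days: 30 + 7 = 37
- 6 months: 180 + 14 = 194
- 1 year: 365 + 30 = 395 (opens at 365 − 30 = 335)
- 2 years: 730 + 45 = 775
- 3 years: 1,095 + 45 = 1,140

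**Which pairs of missed visits matter.** Five visits give 5 × 4 / 2 = 10 pairs. A pair is complete no earlier than the close of the later visit's window.
- Later visit 6 months: 1 pair, day 194
- Later visit 1 year: 2 pairs, day 395
- Later visit 2 years: 3 pairs, day 775
- Later visit 3 years: 4 pairs, day 1,140

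Only the 30-day plus 6-month pair is complete before day 365. From day 194 it is 335 − 194 = 141 days to evaluability and 365 − 194 = 171 days to the end of the endpoint period. Investigator withdrawal has no earliest day.

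**Direction of bias.** Let N be the implanted subjects, L those lost while event-free, x the events observed and m the strokes among the lost that are never collected. The reported rate is x/(N − L). The rate with full ascertainment is (x + m)/N. The reported rate is too low only if m > xL/(N − L).

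Assumptions, none from the documents except 312: all 312 are implanted and in the per-protocol set; x = 25 (25/312 = 8.0%); and 2% to 5% are lost, so L = 6 or 16.

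| L | Reported | Full, m = 0 | Full, m = 1 | Full, m = 2 | Worst case |
|---|---|---|---|---|---|
| 6 | 25/306 = 8.17% | 25/312 = 8.01% | 26/312 = 8.33% | 27/312 = 8.65% | 31/312 = 9.94% |
| 16 | 25/296 = 8.45% | 25/312 = 8.01% | 26/312 = 8.33% | 27/312 = 8.65% | 41/312 = 13.14% |

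The thresholds are 25 × 6/306 = 0.49 and 25 × 16/296 = 1.35. With 6 lost, one uncollected stroke makes the reported rate too low, by 0.16 points. With 16 lost and one uncollected stroke it is too high, by 0.11 points; two are needed to reverse that.

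**The case against.** The rule is stricter than a bare count of missed visits. It also needs three documented attempts per pending visit, one of them by certified letter, and a subject who answers none may be truly unreachable. Day 194 is a lower bound: Protocol 5.11 says "If the visit is not able to be completed during these windows the visit should be completed as soon as possible", the term missed is not defined, and 5.13 makes withdrawal effective only when the sponsor receives the forms. All of this stands. A reader might infer that any two missed visits end follow-up before the endpoint; nine of the ten pairs cannot.

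A reader might also infer that the losses favour the device, because subjects who miss visits may be sicker. The documents do not support a direction. SAP 4.3 keeps every subject with an event in the numerator, so removing event-free subjects raises the rate, while uncollected strokes lower it. Even the one or two strokes in the illustration would mean 1/16 = 6% to 2/6 = 33% of the lost having an ipsilateral stroke in the unobserved period.

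There are safeguards. Protocol 5.13 asks for vital status and stroke or TIA status when a subject refuses visits. Protocol 5.12 asks withdrawing subjects for an end-of-study visit, and the schedule of events includes neurological scales, duplex and adverse events there. SAP 4.10 plans a worst-case analysis and, if necessary, a tipping-point analysis. These limit the harm without closing the gap. The refusal clause is not stated for lost or investigator-withdrawn subjects and has no day-365 target. The end-of-study visit covers only the time up to withdrawal. The sensitivity analyses show what the losses could do but recover nothing.

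**Conclusion.** The point holds in a limited form. An implanted subject's follow-up can end before 1 year without withdrawal of consent, either as lost from about day 194 at the earliest (30-day and 6-month visits missed and contact attempts made) or at any time on the investigator's medical judgment. Neither route requires stroke status to be established to day 365, so some missing primary-endpoint data is avoidable.

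The size of the effect cannot be computed, because the available text gives no loss rate and no event rate. The illustrated shifts rest wholly on assumed values and change sign within a plausible range. The case rests on preventable missing data, not on a demonstrated bias. The sponsor also has a direct interest: in the worst-case analysis each avoidable nonevaluable subject counts as a failure, about 1/312 = 0.32 points.

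**What to change.** - **Protocol 5.13:** do not classify an implanted subject as lost before the 1-year window closes on day 395. Require contact attempts within the 1-year window whatever visits were missed earlier.
- **Protocol 5.12 and 5.13:** extend the vital-status and stroke ascertainment, now stated only for subjects who refuse visits, to lost and investigator-withdrawn subjects. Do this by contact or records through day 365 unless the subject withdraws consent, and send any reported stroke to the CEC.
- **SAP 4.3:** state whether status obtained by contact or records at or after day 335 makes an event-free subject evaluable. The section now lists a case report form, duplex, Rankin and NIHSS as acceptable follow-up. Without this statement, the added ascertainment could contribute events but no event-free subjects.

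The cost is protocol and SAP wording plus a few calls or letters per affected subject. Some attempts will be fruitless, and some dispositions will stay open longer.

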5.14. Subject Study Completion

A subject has completed the study when he/she has completed the 3-year follow-up evaluations. Any subject that does not complete these requirements due to voluntary withdrawal, physician withdrawal, death, or any other reason will be considered as an early withdrawal. In the event of a Technical Failure (no GORE[®] Carotid Stent implanted), the subject will be followed through the 30-day visit and will be considered to have completed the study.

5.15. Explant Procedures

The GORE® Carotid Stent may be explanted during a surgical procedure or as part of an autopsy. Sites are requested to return explanted device to the Sponsor for gross and histological evaluation. Prior to planned or potential device retrieval, contact the Gore associate managing the study to communicate that a specimen is being retrieved from a study subject. A specimen shipping kit will be immediately sent to the Site. The specimen kit provides specific packaging and handling instructions for the specimen and contains a shipping container.

6. Clinical Study Administration

6.1. Device Training

Physician device training will be provided by a qualified Gore Associate. The minimum requirements for physician device training include:

- 1. Didactic training for each investigator at site
- 2. First case for each investigator is supported by a qualified Gore Associate.

6.2. Monitoring

Site monitoring for this study will be provided by:

The Site monitors are qualified by training and experience to oversee the progress of the study at the Site and will ensure that the Investigators and their staff understand and adhere to both the applicable regulatory requirements and the study protocol. In addition, they may assist in resolution of any problems that may arise during the study.

GORE CONFIDENTIAL INFORMATION

Site Initiation

Site initiation will be performed to ensure that each Investigator and his/her staff understands the protocol, applicable regulations, human subject protection requirements, and the Investigator's obligations. This visit will ensure that required documentation with the appropriate approval is in place prior to subject enrollment.

Training on the study EDC System and data gathering requirements may also be done at this time.

Periodic Site Monitoring

Periodic Site monitoring will occur as necessary to ensure continuing adequacy of facilities and adherence to the clinical study protocol, GCP, and applicable regulations and laws that pertain to the conduct of the clinical study. These activities will also review the CRFs and source documentation, the timely submission of accurate records to the Sponsor, and the maintenance of proper records. A report will be written following each Site visit and a follow up letter will be provided to the Site with a summary of findings.

6.3. Device Accountability and Storage

The GORE® Carotid Stent may only be used under the supervision of the Investigator and in strict accordance with this protocol and applicable laws and regulations. The device may only be implanted in subjects who meet the inclusion/exclusion criteria set forth in this protocol and used only as described in this protocol. The Investigator will maintain accurate, detailed records of all devices received from the Sponsor and the disposition of each device. The Investigator will record each device used on the corresponding CRF. The Investigator will notify the Sponsor immediately if any devices are damaged or unaccounted for. The devices must be accessible only to the personnel involved in the study and stored in a secure location.

[figure not shown]
Upon completion or termination of the clinical study or the Investigator's participation in the clinical study, or at the Sponsor's request, the Investigator will return any remaining supply of the device to the Sponsor.

6.4. Core Labs

Core Lab services for this study will be provided by:

Please refer to the Imaging Guidelines for each specific core lab for instructions on submission of images and specific requirements for the images.

6.5. Protocol Deviations

A Protocol Deviation is defined as any change, divergence, or departure from the study design or procedures of a research protocol.t The Investigator is responsible for promptly reporting Protocol Deviations to their reviewing IRB per IRB policy and the Sponsor. The Sponsor will determine the effect of the protocol deviation on the scientific soundness of the clinical study and subject safety and determine if additional reports or actions are required. Additional action may include Site retraining, removal of devices from the Site, and/or Site termination.

The Investigator will not implement any changes to the protocol without first obtaining written agreement from the Sponsor and documented approval from the IRB, except in the event of an immediate hazard(s) to a subject. The Investigator will report the deviation in accordance with the applicable regulations.

6.6. Protocol Amendments

The Investigator will obtain IRB approval on all amendments in a timely manner. The Sponsor will ensure proper training of Investigator and Site staff on all protocol amendments.

6.7. Sponsor Representatives

Sponsor representatives may be present during study procedures to provide technical assistance to the Investigator in the use of the device. The activities of these Sponsor representatives will be supervised by the Investigator.

6.8. Access to Source Data/Documents

Source data are defined as all information necessary for the reconstruction and evaluation of the clinical investigation.

The Investigator will keep all study records, source data and investigational devices available for inspection by the Sponsor, Sponsor's monitors, IRB, and regulatory authorities.

6.9. Study Records Retention

The Investigator will maintain complete, accurate and current study records as required by applicable regulatory requirements. Records will be maintained during the clinical study and for a minimum of two years after the latter of the date on which the study is terminated or completed, or the date the records are no longer required to support regulatory approval of the device. In any event, clinical study records will not be disposed of, nor custody of the records transferred, without prior written Sponsor approval.

Investigator records will include, but not be limited to:

- All correspondence with another investigator, an IRB, the Sponsor, a monitor, or Regulatory Authority, including required reports.
- Records of receipt, use or disposition of a device that relate to:
 - The type and quantity of device(s) received, the date(s) of its receipt, and lot or batch number or code mark.
 - The names of all persons who received, used, or disposed of each device.
- Records of each subject's case history and exposure to the device. Case histories include the case report forms and supporting data including, for example, signed and dated consent forms and medical records, including, for example, progress notes of the physician, the individual's hospital chart(s), and the nurses' notes. Such records shall include:
 - Documents evidencing informed consent and, for any use of a device without informed consent, any written concurrence of a licensed physician and a brief description of the circumstances justifying the failure to obtain the informed consent. The case history for each individual shall document that informed consent was obtained prior to participation in the study.
 - All relevant observations, including records concerning adverse device effects (anticipated and unanticipated), the information and date and condition of each subject upon entering, and information about relevant previous medical history and the results of all diagnostic tests;
 - A record of the exposure of each subject to the investigational device, including the date and time of each use, and any other therapy.
- The protocol, any amendments, and documentation of any deviations from the protocol, including the dates and the reasons for such deviations.
- Any other records that Regulatory Authority requires to be maintained by regulation or by specific requirement for a category of investigations or a particular investigation.
- A certification stating that the US IRB is in compliance with FDA regulations
- A signed Investigator Agreement.
- Any other records as required by the Regulatory Authority, the IRB and the Sponsor.

GORE CONFIDENTIAL INFORMATION

The Investigator will prepare and submit the following reports:

- Withdrawal of IRB approval: The Investigator will report any withdrawal of approval within 5 working days after the Investigator has been notified of the withdrawal.
- Progress reports: Progress reports documenting the procedure, AEs and follow-up data concerning individual subjects will be submitted to the Sponsor on standardized CRFs. The Investigator may also be required to submit progress reports and final reports to the IRB and to the Sponsor summarizing the Investigator's experience during the study.
- UADE Reports: UADEs shall be reported as described in Section 9.
- Protocol Deviations shall be reported as described in Section 6.
- Other: Any other reports as reasonably requested by the Sponsor or required by Regulatory Authority.

7. Data Collection and Submission

The Clinical Data Management System (CDMS) for this study will be provided by:

7.1. Data Collection Methods

This study will report clinical data using the **CDMS** web-based application. The CDMS will be the database of record for the protocol and subject to regulatory inspections. All users will be trained to use the CDMS and will comply with study specific guidelines/instructions as well as applicable regulatory requirements.

Subject data will be collected using protocol-specific electronic case report forms (eCRF). The approved annotated case report forms will be used to create the electronic screens in the CDMS application. Site staff will enter data into the eCRF for transmission to the Sponsor. The Sites will be notified of any amendments to the eCRFs.

7.2. Data Clarification and Correction

All eCRFs will be evaluated upon receipt by the Sponsor. Corrections to missing, incomplete or inconsistent data will be requested from the Site personnel and made though the CDMS. The changes, reason for changes, and person making the change will be documented in the CDMS.

7.3. CRF Completion Schedule

All CRFs should be completed within 14 days of each visit.

8. Risk Assessment

8.1. Potential Risks

The risks associated with the GORE® Carotid Stent for use in carotid arteries are expected to be similar to the risks associated with the use of other commercially available standard of care devices.

Such risks associated with these devices, including the GORE® Carotid Stent include, but are not limited to:

- Deployment and retrieval failure
- Detachment and / or implantation of a component of the system
- Stent deformation
- Stent embolization
- Stent / filter entanglement / damage / dislodgement
- Stent malposition
- Stent migration
- Stent thrombosis / occlusion

Risks associated with these devices including the GORE® Carotid Stent or the interventional procedures include, but are not limited to:

- Allergic reactions to anti-platelet agents / contrast medium
- Aneurysm
- Angina / coronary ischemia
- Arrhythmia
- Arterial occlusion / thrombosis at puncture site or remote site
- Arteriovenous fistula
- Bacteremia or septicemia
- Balloon burst or rupture
- Balloon associated thrombosis
- Bleeding from anticoagulant or antiplatelet medications
- Bradycardia / arrhythmia and other conduction disturbances
- Cerebral edema
- Cerebral hemorrhage
- Cerebral ischemia / transient ischemic attack (TIA)
- Congestive heart failure
- Death
- Drug reactions
- Emboli, distal (air, tissue or thrombotic emboli)

GORE CONFIDENTIAL INFORMATION

- Emergent or urgent endarterectomy surgery (CEA)
- Fever
- Filter fracture
- Filter thrombosis / occlusion
- Fluid overload
- Groin hematoma, with or without surgical repair
- Headache
- Hemorrhage, with or without transfusion
- Hemorrhagic stroke
- Heparin induced thrombocytopenia (HIT)
- Hyperperfusion syndrome
- Hypotension / hypertension
- Infection and pain at insertion site
- Ischemia / infarction of tissue / organ
- Ischemic stroke
- Myocardial infarction (MI)
- Pain and tenderness
- Pseudoaneurysm, femoral
- Reduced blood flow
- Renal failure / insufficiency
- Restenosis of stented segment
- Seizure
- Sepsis
- Severe unilateral headache
- Stroke / cerebrovascular accident (CVA) or other neurological complications (e.g., paralysis, paraplegia or aphasia)
- Surgery required due to device failure
- Temporary or total occlusion of carotid artery
- Thromboembolic episodes
- Thrombophlebitis
- Transient ischemic attacks (TIA)
- Vascular access complications (e.g., bleeding, vessel damage, pseudoaneurysm and infection)
- Ventricular fibrillation
- Vessel dissection, perforation, or rupture
- Vessel spasm or recoil
- Vessel thrombosis (partial blockage)
- Unstable angina pectoris

GORE CONFIDENTIAL INFORMATION

